6.2 Inclusion Criteria

Patients meeting the following criteria will be considered eligible for the study:

Infants will be eligible for inclusion in this study if the St Michael's hospital standard inclusion criteria for cooling are met and additional inclusion criteria for Xenon administration are met.

6.2.1 St Michael's Hospital standard inclusion criteria for cooling

Standard Hypothermia Treatment Criteria for 72 hrs of cooling — all of criteria A, B and C.

A: *Infants ≥ 36.0 weeks gestation (estimated or clinical assessment) with at least ONE of the following:*

- v. Apgar score of ≤ 5 at ten (10) minutes after birth
- vi. Continued need for resuscitation, including tracheal or mask ventilation, at ten minutes after birth
- vii. Acidosis defined as either umbilical cord pH or any arterial, venous or capillary pH within 60 minutes of birth less < 7.00
- viii. Base deficit ≥ 16 mmol/L in umbilical cord blood sample or any blood sample within 60 minutes of birth (arterial or venous blood). If the infant meets criterion A then assess for neurological abnormality using criterion B and C (by trained personnel):

B: *Moderate or severe encephalopathy as evidenced by any of the following:*

- vi. Altered state of consciousness (reduced or absent responses or pathological irritability and hyper responsive and at least ONE or more of the following:
- vii. Hypotonia
- viii. Abnormal reflexes including oculomotor or pupillary abnormalities
- ix. Absent or weak suck
- x. Clinical seizures, as recorded by trained personnel

AND

C: At least 30 minutes duration of amplitude-integrated electroencephalography (aEEG) recording that shows abnormal background aEEG activity. The decision to cool is based on the worst 30 min section of the aEEG, not the best³⁵ or seizures (clinical or electrical) thus meeting ONE of the following:

- v. Normal background with some (> 5 min) electrical seizure activity
- vi. Moderately abnormal activity (upper margin of trace $> 10\mu\text{V}$ and lower margin $< 5\mu\text{V}$)
- vii. Suppressed activity (upper margin of trace $< 10\mu\text{V}$ and lower margin of trace $< 5\mu\text{V}$)

Neonatal Xenon Breathing Device: CoolXenon3 Study	Protocol	CI/2013/4414
	Version	Issue 2, Revision 3
	Issue Date	18 Sept 2019
	Page	38 of 79

viii. Definite seizure activity

6.2.2 Additional inclusion criteria for Xenon

Before being considered for additional inhaled Xenon therapy via the breathing gas mixture, the infant would need to meet further additional entry criteria (all must be met): Before being considered for additional inhaled Xenon therapy via the breathing gas mixture, the infant would need to meet further additional entry criteria (all must be met):

- i. Intubated, ventilated, sedated, being cooled.
- ii. <5 hours old
- iii. Any seizures under control.
- iv. Weight > 2nd centile for gestational age
- v. Stable cardiovascular parameters; Mean arterial pressure >40mmHg.
- vi. Oxygen requirement via mechanical ventilator < 40%.
- vii. Positive End Expiratory Pressure (PEEP) requirement ≤ 8cm H₂O
- viii. Arterial/capillary/venous pCO₂ <7.0kPa (ideally arterial). Venous can be higher if peri-arrest and tissues have been very recently Ischaemic
- ix. Postnatal age <5 hours
- x. Absence of major congenital abnormalities, imperforate anus and in particular any bowel obstruction, congenital abnormalities suggestive of chromosomal anomaly or other syndromes that include brain dysgenesis. Congenital syndromes affecting the brain should be excluded when diagnosed.

6.3 Exclusion Criteria

6.3.1 Exclusion criteria for cooling

- a. Infants expected to be greater than 3 hours of age at the time of starting cooling treatment.
- b. Futility. Where prognosis is considered to be hopeless e.g. no cardiac output for 20 minutes.

6.3.2 Additional exclusion criteria for Xenon

- i. Failure to meet any of the additional inclusion criteria for Xenon listed in section 5.1.
- ii. Patients meeting the following criteria are NOT eligible for the study:
- iii. Presence of any of:
 - a. Major congenital abnormalities
 - b. imperforate anus and in particular any bowel obstruction
 - c. congenital abnormalities suggestive of chromosomal anomaly
 - d. other syndromes that include brain dysgenesis. (Neonates with congenital syndromes affecting the brain should be excluded when diagnosed).

6.4 Prohibited Therapies

Not Applicable.

7.0 Subject Assignment to Treatment Group

The babies entered into the study will be randomised into groups; Xenon+cooling or cooling (standard treatment) alone. Neonates meeting all the entry criteria can be included.

Immediately after enrolment, the patient will be assigned a study ID number, chronologically, from a specified series on an enrolment log specific to the Investigational Site. The Subject's study number and date of enrolment will be entered onto the enrolment log in the Study Binder.

The babies entered into the study will be randomised into two groups on a 1:1 basis. Randomisation will be via sealed opaque envelopes containing details of treatment allocation and [an] identifying adhesive label(s) to be attached to the CRF binder. Neonates meeting all the entry criteria can be included.

8.0 Methods and Procedures

Neonatal Xenon Breathing Device: CoolXenon3 Study	Protocol	CI/2013/4414
	Version	Issue 2, Revision 3
	Issue Date	18 Sept 2019
	Page	39 of 79

8.1 Informed Consent

Informed written consent will be obtained from a parent (only the mother can consent if parents are not married) after a full verbal and written explanation of the study by a named physician or trained nurse such as an advanced nurse practitioner. Such staff will also meet with parents during the intervention period to ensure that they understand the study procedures and continue to consent to participate in the study. Information can be given by local trained staff and consent can also be taken over the phone with the mother if she is unable to be available for the consent process (e.g. cannot be moved shortly after Caesarean Section).

Approval for the study is being obtained from the Regional South West Research Ethics Committee covering St Michael's Hospital.

Most of the patients (>90%) will be born outside the study hospital and are brought to the hospital by a dedicated retrieval team and ambulance from Bristol. The local delivery hospitals will have medical staff (e.g. consultants, specialist registrars, advanced nurse practitioners) trained in consenting for the CoolXenon3 trial. A training log with signatures, a short CV and competency approval will be kept centrally.

Parents will receive a written information leaflet (1 page, short version, Appendix 5) when the infant is eligible for cooling treatment. Staff will discuss CoolXenon3 with parents as soon as practically possible. Parents will be able to speak on the phone to a member of the treatment team if they need further information and help with the consent process. Parents will also be offered the opportunity to speak to members of the treatment team that are picking up the baby for transport.

Trained staff on the transport team can take consent for the study.

A more detailed information sheet regarding the trial will be given to parents after the first conversation or at the earliest suitable time.

Which of the parents can consent to letting the child enter the trial?

- Either parent if they are married
- If the parents are not married, only the mother can consent - provided she is awake and understanding (e.g. not under the influence of anaesthetic drugs)
- If the mother is not in a state to understand the situation and the biological father does currently not have legal parental responsibility he can assent for the trial until the mother is awake/understanding the child's condition and able to decide on consent.

A parent who is eligible to consent can, at any time and without a specific reason, withdraw the child from the study. In this situation, Xenon treatment will then be stopped as soon as possible and medically safe (within minutes).

8.2 Pre-Study

Consent will be obtained as described above from parents of the neonates. Prior to this consent they will have been given an information leaflet describing the study and the discussion will have taken place with a Consultant Neonatologist involved in the study or a trained member of the Transport Team.

8.3 Screening

All infants born in St. Michael's Hospital or retrieved by ambulance from other centres to St. Michael's Hospital Neonatal ICU will have undergone a basic screen of their condition at birth as part of standard procedures, the commonest example being the APGAR scoring system, cord blood analysis and clinical examination. Any infant suspected of being in a poor condition at birth will, by locally present neonatal staff, be assessed for possible cooling as a treatment to limit brain injury using the approved entry criteria (as used in CoolCap and TOBY). Local hospitals will typically contact the St Michael's team within 1 h of age to discuss eligibility, start cooling, transport and potential inclusion in Xenon study. At this point on advice from Bristol, information on the Xenon study can be given to parents.

8.4 Initial Assessment

The following information will be recorded:

8.4.1 Demographics

PATIENT

Neonatal Xenon Breathing Device: CoolXenon3 Study	Protocol	CI/2013/4414
	Version	Issue 2, Revision 3
	Issue Date	18 Sept 2019
	Page	40 of 79

- Date of birth
- LMP last menstrual period
- EDD expected date of delivery
- Gestational age weeks, days e.g. 40 weeks, 3 days
- Race
- Gender
- Weight

MATERNAL

- Years in education
- Labour induced on maternal indication?
- Maternal medical treatment during pregnancy

8.4.2 Patient History and Physical

- Delivery and resuscitation details , Review of Systems, Transport details if retrieved from another centre, Current diagnoses
- Clinical examination

8.4.3 Concomitant Medications

All concomitant medications will be recorded as follows:

- Medication; Start (and Stop date(s) if applicable); Indication; Dose

8.5 Study Phases

The study consists of 3 phases.

8.5.1 Phase 1

Identification of potential subjects – initially using same identification method used in St. Michael's Hospital Bristol to identify infants who would benefit from cooling.

Compliance with all inclusion/exclusion criteria for use of Xenon in addition to cooling (the standard treatment).

8.5.2 Phase 2

Formal recruitment, information supplied to / discussions with parents.

Consent.

8.5.3 Phase 3

Completion of all screening / demographics / baseline data collection immediately pre-Xenon, reintubation with cuffed tube, x-ray for tube placement and blood gas

Administration of 50% Xenon for 18 hours to infant according to randomisation protocol.

Completion of all data collection, serum chemistry and examinations immediately post-Xenon and post-cooling.

8.5.4 Patient Follow-up

8.5.4.1 Short term information and investigations (*before discharge from hospital*):

These are part of routine clinical practice.

1. Survival
2. Duration of hospitalisation
3. Time to full oral feeds, breast, bottle or tube.
4. Hypoxic-ischaemic or other injury² and MRI biomarkers including quantification of NAA in thalamus and fractional anisotropy in white matter using tract based spatial statistics⁴ on MRI scan, which includes Magnetic resonance spectroscopy, undertaken around 48 hours of life and around day 7 of life.
5. Intracranial or intraventricular haemorrhage (on MRI, CT or ultrasound)
6. Major venous thrombosis (on MRI or ultrasound)
7. Resistance Index (Doppler examination of cerebral blood flow velocities)
8. Amplitude integrated EEG (aEEG) continuously recorded until after rewarming, or 82h in cooled-only infants. Assessment of time to normalisation of background activity, seizure occurrence and duration

Neonatal Xenon Breathing Device: CoolXenon3 Study	Protocol	CI/2013/4414
	Version	Issue 2, Revision 3
	Issue Date	18 Sept 2019
	Page	41 of 79

9. Pulmonary hypertension needing treatment
10. Pulmonary haemorrhage
11. Pneumonia
12. Pulmonary air leak
13. Systemic hypotension needing inotropic support
14. Prolonged blood coagulation time assessed before Xenon and at ~24 hours and/or at clinically indicated timepoints
15. Cardiac arrhythmia (not temperature induced low Heart Rate)
16. Thrombocytopenia (platelets <100,000/ul)
17. Culture proven sepsis
18. Necrotising enterocolitis or intestinal perforation, medical, radiological or surgically proven
19. Plasma markers of global (increased lactate dehydrogenase (LDH)) or cardiac compromise (increased cardiac Troponin T (cTnT)) or plasma lactate
20. Renal failure treated with dialysis

8.5.4.2 Short term assessment neurological evaluation will include

1. Time to recovery after birth of a normal background aEEG¹
2. MRI scan before 14 days of life^{2,4,35}
3. Peak LDH value within 72h of life^{5,36}
4. First plasma glucose after birth (usually from cord blood)
5. Age in hours after birth when plasma lactate has declined to <5mmol/l
6. Number and type of inotropic drugs needed during stay on the neonatal intensive care unit (typically the period from birth to 3-5 days of age) and the total duration in hours of any inotropic support
7. Number of anticonvulsant drugs given during stay on the neonatal intensive care unit.
8. Amount and duration of sedation (e.g. plasma morphine levels) while ventilated mechanically on the neonatal intensive care unit.
9. Stress levels (saliva, plasma and urinary cortisol and adrenocorticotropic hormone)
10. Age at full oral feeds (breast or bottle or tube)
11. Outcomes of neonatal hearing screening before 14 days of life
12. Clinical examination at birth, at 7 days of age and at discharge including weight and head circumference

8.5.4.3 Long term follow up (at 18 months)

Neurodevelopmental follow up is a part of the routine follow up of infants with Neonatal Encephalopathy. Bayley III examination at 18 months of age is used to compare the results from this study with our large local patient database and previous randomised controlled trials (CoolCap, Gluckman 2005; TOBY, Azzopardi 2009)^{13,14} where Bayley II was also used: we were a main recruiting centre for these trials.

Disability will be defined as any of:

- Bayley III Cognitive and Language Composite score less than 85.
- Bayley III Motor Composite score less than 85
 - Bayley III will also be expressed as developmental quotients (DQ) calculated from Developmental Age scores as this allows a larger range of score for those functioning at a low level³⁷In this study a Bayley III assessment¹¹ will be undertaken and data will be converted to Bayley II MDI and PDI for comparison with historical controls.
- Bilateral cortical visual impairments.
- Hearing loss needing amplification > 40 dB.

8.5.4.4 Additional follow up

We will do short-term (14 days), intermediate (6 months) and long-term (18 months survival) follow-up.

8.6 Study Data

All the patient study information will be coded by patient study number, anonymised and securely stored until the study is complete. Electronic data will be stored on a secure portion of a Hospital Trust computer. The Chief Investigator will ensure that all the patient identifying details have been removed prior to statistical analyses being undertaken.

Neonatal Xenon Breathing Device: CoolXenon3 Study	Protocol	CI/2013/4414
	Version	Issue 2, Revision 3
	Issue Date	18 Sept 2019
	Page	42 of 79

The identification key linking study numbers to patient details will be kept by the CI ([name]) in a locked filing cabinet in a locked office in the Neonatal Neuroscience office of St. Michael's Hospital Bristol, which also has two separate secure swipe card entry systems.

8.7 GP Notification

The General Practitioner will be informed via a letter of the participation of the infant in the study when the infant is discharged from hospital.

8.8 Definition of End of Study

The end of the trial as a whole will be when all recruited participants have completed the treatment and follow-up period **and** all data has been collected and analysed, with data queries answered.

9.0 Assessment of Safety

9.1 Data Review Group

An IDRG will be set up and appropriately constituted with clearly defined terms of reference. Their role will be to independently review the safety of the study after every 8th Xenon patient has been recruited and in the light of this make appropriate recommendations to the study team.

The IDRG will also meet in the event of a death, regardless of cause. This meeting will take place within ~14 days of the death and recruitment into the study will continue in the meantime. This meeting could be in person or take the form of a teleconference. In our initial study of Xenon+cooling a partial external committee met at intervals of every other baby enrolled. For the CoolXenon2 study, the IDRG met after every 4th Xenon patient had been recruited.

In the CoolXenon1 or CoolXenon2 studies there were no significant physiological or biochemical changes or other problems attributable to the Xenon gas or the use of the NXBD. An identical NXBD will be used in this study.

Given the excellent safety record of the previous two studies involving Xenon use and the NXBD, it is considered appropriate that for this study the IDMG should meet after every 8th Xenon patient is recruited.

9.3.1 Reasons for stopping Xe delivery before the 18h timepoint

Cardiovascular problems sometimes present as untreatable hypotension. In this situation the heart has also suffered hypoxia-ischaemia and sometimes it is impossible to maintain a perfusion pressure even with the use of maximum inotropic support.

Another problem would be if the neonate develops a very high oxygen fraction (up to 100%) in the breathing gas over time, >40% according to the study entry criteria. An example would be those who have aspirated meconium.

9.3.2 Stopping rule

Mortality since cooling became standard of care at St Michaels hospital (inborn and outborn) fell from 34% to 10.3% (17 out of 165 infants born since December 2006 and undergoing cooling died). If, with this (10.3%) underlying mortality, the two first infants receiving Xenon die, the probability that this is a random event is very small ($p=0.01$) and recruitment should be stopped and the protocol reviewed. The same applies if 2 out of the first three babies randomised to Xenon die ($p=0.03$).

Thereafter, (n is the number of 'Xenon' babies included in the study):

n	Number of Deaths	Action
2	2 of 2	Stop study and review
3	2 of 3	Stop study and review
4	3 of 4	Stop study and review
5	3 of 5	Stop study and review
6	3 of 6	Stop study and review
7	3 of 7	Stop study and review
8	3 of 8	Stop study and review
9-14	4	Stop study and review
15-22	5	Stop study and review
23-26	6	Stop study and review

This stopping rule is based on two considerations:

- i. Probabilities given 10.3 % mortality without Xe
- ii. Stricter rule with more babies included

Neonatal Xenon Breathing Device: CoolXenon3 Study	Protocol	CI/2013/4414
	Version	Issue 2, Revision 3
	Issue Date	18 Sept 2019
	Page	44 of 79

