3.3 Secondary Endpoint

The following potential predictors of outcome will be used:

- a. Time to recovery after birth of a normal aEEG¹
- b. MRI scan around 48hours and around day 7 of life, to assess lesions consistent with hypoxic-ischaemia,² absolute quantification of thalamic NAA and white matter fractional anisotropy using tract based spatial statistics.^{3,4,35}
- c. Peak LDH value within 72h of life^{5,36}
- d. Resistance Index (RI).

We will also collect data on:

- e. Plasma glucose at birth (in cord blood)
- f. Age in hours after birth when plasma lactate has fallen to 5mmol/L
- g. Different inotropic drugs needed and the total duration in hours of any inotropic support

Neonatal Xenon Breathing Device: CoolXenon3 Study	Protocol	CI/2013/4414
	Version	Issue 2, Revision 3
	Issue Date	18 Sept 2019
	Page	21 of 79

- h. Number of anticonvulsants given
- i. Amount and duration of sedation (e.g. plasma morphine level), stress level (plasma, salivary, urine cortisol level and adrenocorticotropic hormone)
- j. Age at full oral feeds (breast or bottle or tube)
- k. Neonatal hearing screening result before 14 days of life
- l. Clinical examination at birth, at 7 days of age and at discharge including weight and head circumference

Neurodevelopmental follow up is a part of the routine follow up of infants with HIE, Bayley III examination at 18 months of age.

Disability will be defined as any of:

- m. Bayley III Cognitive Composite score less than 85.¹¹
- n. Bayley III Motor Composite score less than 85 (Bayley scores will also be expressed as a Developmental Quotient (DQ) calculated from developmental age scores as this allows a larger range of scores for those functioning at a low level)³⁷
- o. Bilateral cortical visual impairments
- p. Hearing loss needing amplification > 40dB.

In addition any Adverse Events will be recorded and criteria have been devised for stopping the study early if necessary. The IDRG will review data when 8, 16 and 24 infants have undergone Xenon treatment.

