10.2 Interim Analysis and Stopping Rules

No interim analyses are planned. Stopping rules are detailed in Section 9.3.1.

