13.0 Discontinuation of Study

See Section 9.3.1.

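### Sections 10.2 and 13.0 cite 9.3.1 for stopping the study when the rule is in 9.3.2, and 9.1 and 9.3.2 differ on recruitment after a death that meets the mortality table

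*Protocol*

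**What the plan says.** Section 3.3 announces that "criteria have been devised for stopping the study early if necessary". Three later sections bear on where those criteria are and what they require.

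- **Where the rule is said to be.** Section 10.2 reads "No interim analyses are planned. Stopping rules are detailed in Section 9.3.1". The whole of section 13.0, on discontinuing the study, is "See Section 9.3.1".
- **What 9.3.1 and 9.3.2 contain.** Section 9.3.1 is headed "Reasons for stopping Xe delivery before the 18h timepoint". It describes untreatable hypotension and a rising oxygen requirement in an individual infant. Section 9.3.2 is headed as the stopping rule. It gives a table of deaths against the number of Xenon infants, and every row carries the action "Stop study and review". For two deaths in the first two Xenon infants it adds that "recruitment should be stopped and the protocol reviewed", and it applies the same to two of the first three.
- **What happens to recruitment after a death.** Section 9.1 says "The IDRG will also meet in the event of a death, regardless of cause". It continues: "This meeting will take place within ~14 days of the death and recruitment into the study will continue in the meantime".

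**The concern.** Section 13.0 is the protocol's section on ending the trial, and it consists of a single pointer. Anyone who follows it, or the pointer in 10.2, reaches criteria for one infant's treatment and no criterion for the study.

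The second matter is what staff do about recruitment in the days after a death that meets the table. Section 9.1 tells them to go on recruiting until the IDRG has met. Section 9.3.2 tells them to stop. Neither section refers to the other. The question would arise only when Xenon deaths are accumulating, which is when the rule is needed.

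**Working it through.** **Cross-references.** No arithmetic applies. Sections 10.2 and 13.0 both name 9.3.1. Section 9.3.1 contains no death count, no boundary and no action on recruitment. Section 9.3.2 contains all three.

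**Inputs for the overlap between 9.1 and 9.3.2**

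- Baseline mortality p = 17/165 = 10.3% (section 9.3.2).
- Boundary b(n) in Xenon-group deaths (section 9.3.2): 2 at n = 2–3; 3 at n = 4–8; 4 at n = 9–14; 5 at n = 15–22; 6 at n = 23–26.
- Alternative mortality: 7% (CoolXenon2, section 1.0), and 20.6% = 2 × 10.3% (assumed, to represent harm).
- 26 infants per group, 52 in total (section 4.10 and Protocol Summary); recruitment up to two years (Protocol Summary).

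**The plan's own figures, reproduced first**

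- Two deaths of two: p² = 0.103² = 0.0106, printed as 0.01.
- At least two of three: p² + 2p²(1 − p) = 0.0106 + 2 × 0.0106 × 0.897 = 0.0296, printed as 0.03.

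Both are correct.

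**Which deaths fall under both sections.** The smallest boundary is two, so a single death cannot meet the table. Control-group deaths do not count towards it. Because b(n) never falls as n rises, a table checked after every Xenon infant can be first met only when a new Xenon death occurs. That death is also a death under 9.1, so each first crossing comes under both instructions.

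**How often that happens.** Let f(n, k) be the probability of k deaths among the first n Xenon infants with the table not yet met:

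f(n, k) = f(n − 1, k)(1 − p) + f(n − 1, k − 1)p, for k < b(n).

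The probability reaching b(n) at each n is removed and added up. This assumes that each outcome is known before the next infant is counted.

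| Xenon mortality | Met by n = 3 | Met by n = 8 | Met by n = 26 |
|---|---|---|---|
| 7% | 0.0140 | 0.0242 | 0.0401 |
| 10.3% | 0.0296 | 0.0577 | 0.1186 |
| 20.6% | 0.1098 | 0.2483 | 0.5801 |

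**Infants affected per event**

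- Recruitment over two years: 52/730 × 14 = 1.0 infant in 14 days, of whom 26/730 × 14 = 0.5 would be in the Xenon group.
- Recruitment over one year (assumed): 52/365 × 14 = 2.0, of whom 1.0 would be in the Xenon group.

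**The case against.** The strongest reply is that a specific rule ordinarily overrides a general one. Section 9.1 sets the default after a death, and 9.3.2 governs once its counts are reached. The working supports this: if 9.1 always prevailed, the instruction in 9.3.2 to stop recruitment could not take effect when its boundary is reached, only after the IDRG had met. Reading 9.3.2 as the exception gives both sections effect. That reading is plausible, but it remains an inference, because 9.1 is worded without exception.

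The absence of a linking statement is also not fully checkable. The text between 9.1 and 9.3.1, where the contents list places the composition of the IDRG, was not available to this review. Nor were the IDRG's terms of reference, which 9.1 mentions. Either could settle precedence. Neither would alter the wrong references in 10.2 and 13.0.

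On those references, it is fair to say that the correct rule is in the very next subsection, so a careful reader would probably find it.

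Three stronger readings are not supported:

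- A reader might infer that the two instructions clash after every death. Most deaths would not meet the table.
- A reader might count clashes at the planned IDRG reviews at 8, 16 and 24 Xenon infants. By such a review, the death that reached the boundary may be long past and its 14-day interval closed.
- A reader might take the 12% as a fault in the stopping rule. It is only the frequency with which the two instructions overlap.

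**Conclusion.** The cross-reference error is certain: 10.2 and 13.0 point to the wrong subsection for stopping the study. It is an error in operative safety text, though a simple one.

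The difference between 9.1 and 9.3.2 is real but narrow. It concerns only the death that first meets the table, with a probability of about 12% at 10.3% mortality, 4% at 7% and 58% at 20.6%. The consequence per event is small, about one infant randomised in 14 days over two-year recruitment. These figures assume a check after every Xenon infant with outcomes known in sequence, and even recruitment. The statement that nothing settles precedence is limited to the text available.

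Both matters should be corrected. Neither affects the boundaries, the endpoints or the analysis.

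**What to change.** Change the reference in 10.2 and in 13.0 from 9.3.1 to 9.3.2. Add one sentence, in 9.1 or 9.3.2, stating which instruction on recruitment applies when a death meets the table. Which one it should be is for the sponsor and the IDRG to decide. If the section on the IDRG's composition or its terms of reference already says so, a cross-reference is enough.

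The cost is two section numbers and one sentence. The table, its printed probabilities, data collection and analysis do not change.

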Neonatal Xenon Breathing Device: CoolXenon3 Study	Protocol	CI/2013/4414
	Version	Issue 2, Revision 3
	Issue Date	18 Sept 2019
	Page	5 of 79

Population Size	52 babies in total
Structure	Prospective randomised comparative outcome study
Duration of Participation	Xenon administration period of 18 hours. Recruitment period up to two years from start of study. Short and long term monitoring until 18 months of age. Therefore total study duration 3.5 years.
Definition of End of study	The end of the trial as a whole will be when all recruited participants have completed the treatment and follow-up period and all data has been collected and analysed, with data queries answered.
Method of Assignment	Neonates meeting all entry criteria can be included.
Randomisation	Patients will be randomised between cooling (standard treatment) and Xenon+cooling groups on a 1:1 basis.
Statistical Analysis	This is a randomised pilot outcomes study. The statistician for this study is [name] who has also advised on all the preliminary experimental Xenon work and the previous two clinical feasibility studies and a recent clinical evaluation of the Bayley examination which is used in this study. ⁸⁻¹¹
Adverse Events	Volunteered and Elicited

Protocol	CI/2013/4414
Version	Issue 2, Revision 3
Issue Date	18 Sept 2019
Page	6 of 79

SECTION	CONTENTS	PAGE
	Confidentiality Statement	2
	Protocol Summary	3
	Approvals	11
	Declarations and Signatures of Investigators	12
	Schematic of Study Design	13
	Study Administration	14
	List of Abbreviations	15
1.0	Overview	17
2.0	Background and Introduction	18
2.1	Background	18
2.2	Review of Literature	18
2.3	Rationale for the Study	19
3.0	Objectives	20
3.1	Primary Objective	20
3.2	Primary Endpoint	20
3.3	Secondary Endpoint	20
3.4	Tertiary Endpoint	21
4.0	Study Design	22
4.1	Study design and procedures	22
4.1.1	St Michael's hospital standard inclusion criteria for cooling	22
4.1.2	Exclusion criteria for cooling in the CoolXenon2 study	23
4.1.3	Additional inclusion criteria for Xenon	23
4.2	Consent	23
4.2.1	Which of the parents can consent to letting the child enter the trial?	24
4.3	Randomisation	24
4.4	Clinical Management	24
4.4.1	Specific clinical management of cooling group	24
4.4.2	Specific clinical management of Xenon+cooling group	24

Neonatal Xenon Breathing Device: CoolXenon3 Study	Protocol	CI/2013/4414
	Version	Issue 2, Revision 3
	Issue Date	18 Sept 2019
	Page	7 of 79

4.5	Further information on the oxygen fraction in the breathing gas mixture	25

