4.10 Group size

Twenty-six babies will be recruited into each group (cooling+Xenon vs. cooling alone) at random. The cooling will be applied as standard treatment if cooling criteria are met. Addition of Xenon in combination with this underlying cooling will take place in the group randomised to receive cooling + Xenon.

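### The mortality stopping rule counts Xenon infants by order of entry in its prose but by the running number included in its table, so the two can disagree when infants enter before a death is assessed

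*Protocol*

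**What the plan says.** Section 9.3.2 of the protocol takes a background mortality of 10.3% ("17 out of 165 infants born since December 2006 and undergoing cooling died"). Its first boundary is that if "the two first infants receiving Xenon die, the probability that this is a random event is very small" (p=0.01), recruitment should stop and the protocol be reviewed. The second is "The same applies if 2 out of the first three babies randomised to Xenon die" (p=0.03). Both name infants by their place in the sequence.

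A table then follows, in which "n is the number of 'Xenon' babies included in the study". It repeats the rows 2 of 2 and 2 of 3, and then requires 3 deaths at n = 4 to 8, 4 at n = 9 to 14, 5 at n = 15 to 22 and 6 at n = 23 to 26. The section does not say when n is read, whether n is limited to infants whose outcome is known, or over what period deaths count.

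Section 9.1 has the Independent Data Review Group (IDRG) meet after any death: "This meeting will take place within ~14 days of the death and recruitment into the study will continue in the meantime".

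**The concern.** A binomial boundary such as 3 deaths in 8 assumes that all 8 infants have had the chance to die. A running count of infants included does not meet that assumption. The newest entrants add fully to n and almost nothing to the deaths.

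Because recruitment continues after a death, a later entry can move the table to a row with a higher death number before a death occurs or is assessed. The same facts, such as three deaths among the first eight infants, then lead to a stop or to continuation according to whether a ninth infant happens to have entered. For the first three infants the prose and the table can give the IDRG opposite instructions. What is at stake is mainly delay: some further infants exposed before a review that the rule, read by order of entry, would already have required.

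**Working it through.** **1. The protocol's own figures.** Background mortality is 17/165 = 0.103. For 2 deaths in 2, 0.103² = 0.0106. For at least 2 in 3, 3 × 0.103² × 0.897 + 0.103³ = 0.0285 + 0.0011 = 0.0296. These round to the stated 0.01 and 0.03. Both hold for a fixed set of infants, all followed.

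**2. What one more entry does at each step** (binomial tails at 10.3%).

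| Step | Deaths that stop before the step | Tail probability before | Same deaths after the step | Deaths then required | Tail at the new requirement |
|---|---|---|---|---|---|
| 3 to 4 | 2 | 0.030 | 0.055 | 3 | 0.004 |
| 8 to 9 | 3 | 0.041 | 0.057 | 4 | 0.009 |
| 14 to 15 | 4 | 0.048 | 0.061 | 5 | 0.014 |
| 22 to 23 | 5 | 0.069 | 0.081 | 6 | 0.026 |

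Delay matters only when enrolment crosses one of these four steps. At the first, the prose still calls for a stop, so prose and table conflict. At the other three only the table speaks.

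**3. Chance of ever crossing the table at 10.3% mortality** (200,000 simulated arms of 26). By order of entry it is about 0.118 whatever the delay. With n read at the moment of death and one, two or three Xenon infants entering between an infant's entry and its death, the table alone gives 0.096, 0.078 and 0.068. With the first-two and first-three prose honoured as well, it gives 0.105, 0.094 and 0.085. At 30% mortality the table alone falls from 0.89 to 0.88, 0.87 and 0.86.

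**4. Delay in calendar time.** The protocol gives the arm size ("Twenty-six babies will be recruited into each group") and the duration ("Recruitment period up to two years from start of study"). Even accrual is then 24 × 30.44 / 26 = 28.1 days per Xenon infant. Time to death is not given. I assume exponential delays with mean 3, 7 or 14 days, exponential gaps between entries, and true Xenon mortality of 10.3%, 20% or 30%. I ran 40,000 simulations per setting. The comparison is the table by order of entry against the running table plus the prose, both read at the same moments. Percentages are of trials that stop under the entry-order rule; ranges run over the three delays.

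| Mortality | Read at death: late | Read at death: never | Read 14 days later: late | Read 14 days later: never |
|---|---|---|---|---|
| 10.3% | 0.9–5.0% | 1.1–4.6% | 5.1–8.4% | 5.9–9.7% |
| 20% | 1.4–6.8% | 0.5–2.0% | 6.4–11.1% | 2.1–3.9% |
| 30% | 1.5–6.5% | 0.1–0.5% | 5.6–10.2% | 0.7–1.0% |

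Separate runs of the same model put late stops at about 0.5% to 7% (read at death) and 5% to 11% (read 14 days later), so these are orders of magnitude. Late stops came on average 2.5 to 4.3 Xenon infants later with the prose honoured, and 2.9 to 5.0 later for the table alone: roughly 3 to 5. The overall chance of stopping fell by 0.1 to 2.2 points with the prose honoured and by at most 2.8 points for the table alone.

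**The case against.** The case against is substantial, and several parts of it stand.

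- A reader might infer that a later entry cancels a boundary already met, with 2 of the first 3 as the example. The text does not support that. The prose fixes those infants by sequence and calls for a stop, and nothing says this lapses when a fourth enters. A boundary reached while n is still in its row has already triggered. For the first three infants the defect is a conflict between prose and table.
- A reader might also infer that early-harm protection is lost mainly at the first rows. Those are the rows the prose protects.
- Much larger effects appear if the table is taken alone and read only at a meeting 14 days after each death: about 20% to 43% of 2-of-first-3 patterns would no longer show. But 9.1 sets an approximate upper limit for the meeting. It does not say that the table is applied only then, or with that day's n.
- Trials that never stop are most frequent at 10.3%, the rule's own background rate, where a stop is a false alarm. At 30% they are about 1% or fewer.
- The table prints no probabilities, so it cannot be called looser than a stated error rate. The two printed values belong to the prose and are correct.
- The IDRG meets after every death whatever the row, so an independent review takes place in any case.
- The later rows can be read by order of entry, by analogy with the prose. That is reasonable, but the definition of n says otherwise, and no prose covers the steps after row 3.

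**Conclusion.** The point holds as an internal inconsistency in a safety decision rule with a small numerical effect. Section 9.3.2 uses two counts. They conflict at row 4, and from row 9 on the literal table can miss a boundary that the first n infants meet.

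The sizes rest on assumptions the protocol does not supply: time to death, even accrual over 24 months, and the moment at which the table is read. Longer delays would enlarge the effect. With a fixed 30-day delay at 10.3% mortality, the chance of stopping falls from 0.119 to 0.107 with the prose honoured (0.099 for the table alone). The main consequence is an occasional stop a few infants late in an arm of 26. The case for changing the text is that a mortality rule should give one answer to one set of facts, and that the correction costs almost nothing.

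**What to change.** Reconcile the prose and the table in 9.3.2 by redefining n, for example: at each death, the table is applied to the first 2, 3, … n Xenon infants in order of entry, counting all deaths known among them; a row once met stays met, whatever number has since been included. Leave the death numbers as they are, and carry the same sentence into the IDRG's terms of reference.

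The cost is one sentence in each place. Stop-and-review will be called slightly more often, including for a late death in an early infant. At 10.3% mortality the chance of crossing is then about 0.118 by order of entry, which is what the table already gives when there is no delay.
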